2.5.1 MCDS-Therapy participant visit schedule (modified from Protocol version)

	Stage 1: Dose ti	: Dose titration participant		Stage 2: Treatment phase participants		
Stage of trial	Visit	Timepoint		Visit	Timepoint	
Consent/screening	Consent Screening visit 1*			Consent Screening visit		
and eligibility	Screening visit 2*	Up to 2 consent	8 days post	Screening visit 2*	Up to 28 days post consent	
Basalina	Visit 1*	0	Months	Visit 1*	0	Months since
observation	Visit 2	6**	since Baseline	Visit 2	6	Baseline observation
phase	Visit 3*	12***	observation			
	Visit 1.1*	0	Weeks			
	Visit 1.2	2	since start			
Dose titration	Dose evaluation telephone calls	1 -11	titration phase			
phase	Visit 1.3	3				
	Visit 1.4	6				
	Visit 1.5	9				
	Visit 1.6	12				
	Visit 2.1*	12*	Months	Visit 2.1*	0	Months
	Visit 2.2	15	since start	Visit 2.2	3	since start
Treatment phase	Visit 2.3	18	of Dose	Visit 2.3	6	of
	Visit 2.4	21	phase	Visit 2.4	9	phase
	Visit 2.5	24		Visit 2.5®	12	h
	Visit 2.6 ^Δ	27				
Optional extended	Visit 2.7 ^a	30				
treatment phase	VISIT 2.8 ⁴	33				
	VISIL 2.9	50				

*Visits which may coincide with the preceding or proceeding visit: - Screening visit 1 and 2/Visit 1 baseline observation; Visit 3 baseline observation/Visit 2.1 treatment phase

**6 month visit may be missed for participants who have experienced delays to their visit schedule due to COVID-19 halt to the trial

***12 month visit may be rescheduled to 18 month visit for participants who have missed the 12 month visit due to COVID-19

^A This is an optional visit subject to an additional informed consent

[®] Visit 2.5 in Stage 2 and visit 2.9 in Stage 1 must occur no later than 31st January 2024.

2.6 Sample size and power

The sample size was chosen on the basis of the feasible number of patients that could be recruited to the trial in the specified time period. No statistical criteria were used to choose the sample size.

The trial was initially designed to have a cohort of 12 participants in Stage 1, the dose determination stage, and a cohort of 28 participants in the treatment stage, Stage 2. However due to the COVID-19 pandemic delays, this has been amended to Stage 1; N=11 and Stage 2; N=29. The overall sample size remains the same (N=40)

2.7 Overview of MCDS-Therapy Clinical Trial (from Protocol)

*The 12 month baseline observational visit may be rescheduled to a 18 month visit for participants who have missed the 12 month visit due to COVID-19 (Stage 1 UK participants only).

[^] To aid with study participant retention due to COVID 19, with discussion with the CI, the 12 month baseline observational visit window can be up to 12 months and 8 weeks. This will be assessed on a case by case basis through discussion with the site PI^a with approval from the CI and the NCTU team notified.

Eligible Stage 1 participants may continue treatment for further 12 months (up to 36 months) subject to a separate informed consent at visit 2.5.

Last Patient Last Visits in Stage 1 and Stage 2 must be completed by 31st January 2024.

3 Study Population

3.1.1 Screening, eligibility, and recruitment

Screening data, number assessed for eligibility, number not meeting eligibility criteria (with reasons), number declining participation (with reasons) and any other reasons for not entering the study will be reported.

3.1.2 Protocol deviations

Protocol deviations including missed safety assessments; incorrect dose escalations; missed study assessments; participants not using IMP as prescribed; and lack of compliance will be reported.

Example Table: Line listing of protocol deviations

Trial ID	Deviation type	Major/minor	Details
	Ineligible/Consent/Treatment not given as per- protocol/Withdrawal from treatment by investigator/Withdrawal from treatment due to participant choice/Use of prohibited concomitant medication/Study procedures/Visit schedule		

3.1.3 Follow-Up

Participants have the right to withdraw from the trial at any time without having to give a reason. If a trial participant withdraws from the trial all data collected to the point of withdrawal will be retained. Consent/assent will be sought to allow this.

The number of patients withdrawing from trial specific follow-up visits, the number withdrawing from any follow-up data to be collected and the number lost to follow up, with timing of withdrawal will be reported.

3.1.4 Participant flow through trial

Patient flow through the trial will be presented using a CONSORT diagram (example below). Information will be provided on numbers and reasons (where appropriate) for: screened patients not being eligible; eligible patients not being consented; patients found to be ineligible after consent; patients not evaluable for the primary endpoints; withdrawal from follow-up; withdrawal of consent and all protocol violations.

Example Figure: CONSORT flow diagram

3.1.5 Baseline characteristics

Demographic, clinical and surgical characteristics recorded at the first visit during the baseline observation period will be summarised. Categorical data will be presented as frequencies and percentages, continuous data will be presented as number of patients, mean, median, standard deviation, minimum, maximum and range.

Demographic characteristics: age, sex, height (or length if <2 years old), sitting height in children >=5 years old, crown-rump length (CRL) in children <5 years old.

Clinical characteristics: age at onset of first symptoms, pain at diagnosis of MCDS (yes/no), current frequency of pain, joints affected with pain, surgical interventions to manage MCDS symptoms (yes/no), bone age, head/neck of femur angle.

Example Table: Patient demographics at baseline

	n=X	
Sex		
Male		
Female		
Age (years)		
Median		
Mean		
Median BMI		
Blood pressure (mmHg)		
Systolic		
Diastolic		

3.1.6 Treatment received

Stage 2 participants will receive Tegretol[®] for a 12 month period. Dosage will be calculated according to the participant's weight. As the trial is recruiting paediatric participants, participants will be weighed every 3 months as part of the physical examination and dose adjusted accordingly to ensure the appropriate dose is given to the participants as they grow. For Stage 2, participants CBZ will be titrated to a dose of 20mg/kg.

Participants will be initiated on a daily CBZ dose of 5mg/kg/day, divided into two separate doses. If the current dose is tolerated following seven days of treatment, the daily dose will be increased by 5mg/kg/day for a further seven days. The dose level will be increased every seven days until a maximum dose of 20mg/kg/day or MTD is achieved.

At weekly intervals and until they reach a stable dose, participants will receive a dose evaluation telephone call to determine if the current dose has been tolerated. Participants are asked to provide information regarding drug side effects, AEs, changes to concomitant medication, drug compliance and details of missed doses; a Diary is provided in which to record this information between calls/visits. All dosage decisions, IMP side effects, AEs and any changes to concomitant medication noted during the dose evaluation calls are recorded in the appropriate eCRF within the trial MACRO database.

If the participant reports side effects/AEs of significant concern to the clinician which are suspected to be related to the IMP, they are invited for further laboratory safety blood assessments and review. If the

participant reports severe side effects which prevent adherence to the trial protocol or in the opinion of the clinical investigator deem the participant not suitable to continue participation, then CBZ will be permanently discontinued, and the patient withdrawn from the trial. Participants who do not tolerate dosing will be kept on a lower dosing or dosing reduced.

For each participant, the following will be reported:

- 1. Initial prescribed daily dose (mg/kg) of CBZ and form (tablet/suspension).
- 2. Daily Dose (mg/kg) and prescribed daily dose (mg or ml, depending on CBZ form) will be shown graphically over the treatment period.
- 3. Compliance will be reported as the number of missed CBZ doses reported at each visit or dose evaluation phone call together with the percentage of the prescribed daily dose taken.
- 4. MTD

4 Statistical considerations

4.1 Timing of analyses

The *Stage 1 safety review* was conducted to formally agree the IMP dose regimen to be implemented in Stage 2 of the study, report to DMC dated 25/10/2021. The final analysis of Stage 2 will take place after data cleaning following the end of trial – this is defined as the date of last data collection for the last participant and is expected to be spring 2024.

4.2 Analysis populations

There will be two analysis populations:

1. Participants who have completed the baseline observation period and have received at least one dose of CBZ.

2. Participants who have completed their baseline observation period and have been prescribed, on average, at least 15 mg/kg of CBZ over their first 12 -months of treatment, i.e. a dose which is at least 75% of the dose recommended from Stage 1. Note that some participants will have longer than 12 months of treatment.

Adverse events will be reported for all participants who start their baseline period.

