8.8.6 Dose finding review

An interim safety analysis will be conducted when at least six patients reach their MTD, which will allow modification of the regimen if required. The review will be led by the CI, Sponsor will be consulted and agreement from the trial IDMC will be sought. The review will be based on laboratory

safety assessments, adverse events and pain questionnaires. Treatment of the remaining stage 1 participants will not be delayed while this review is ongoing.

Once all 11 participants have reached 6 months (or those who are still continuing / not withdrawn), a safety review will be conducted to formally agree the IMP dose regimen to be implemented in Stage 2 of the study. Data to be reviewed includes laboratory safety assessments, adverse events, and pain questionnaires. The review will be led by the CI, Sponsor will be consulted and agreement from the trial IDMC will be sought.

Handling and review of data for both safety reviews will be performed in accordance with the trial Data Management Plan and Statistical Analysis Plan.

Participants who do not tolerate dosing will be kept on a lower dosing or dosing reduced. The inclusion of such patients in the final efficacy analysis will be discussed and evaluated case by case by the TMG with input from the IDMC if required.

Table 10 Timing and Frequency of reviews

Review	Time	Outcomes	IDMC agreement required
Interim safety analysis	First 6 patients reach MTD or 20mg/Kg	Primary outcome (SAFETY): Laboratory safety assessments, adverse events, pain scores and physical examinations collected post IMP administration.	Yes
Safety Review	11 th patient reaches the 6 month time point (or those who are still continuing / not withdrawn),	Primary outcome (DOSE) : Outcome of dose-titration safety review at 6 post IMP treatment initiation.	Yes, required to agree dose for Stage 2
Completion of Stage 1 safety analysis and Pain analysis	12 months from Baseline (when last patient recruited has reached 12 month time point) A further safety analysis will be presented to the IDMC on completion of Stage 1	 Primary outcome (SAFETY): Laboratory safety assessments, adverse events, pain scores and physical examinations collected post IMP administration. Secondary outcome (PAIN): Alteration from baseline in pain perception over 12 months as measured by: PEDSQL Pain Coping Inventory PEDSQL Pain Questionnaire 	No, to be presented at next IDMC meeting following analysis

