11 STATISTICAL CONSIDERATIONS

11.1 Analysis Population

There will be two analysis populations:

- Patients who have completed the baseline observation period and have received at least one dose of CBZ
- Patients who have completed the baseline observation period and have received at least 75% of planned CBZ doses over the 12 -month treatment period

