1.2 Stage 1 summary

The primary objective of Stage 1 was to assess the safety and tolerability of CBZ in the treatment of children with MCDS who are ambulant but have not yet reached skeletal maturity (open epiphyses) and to determine an appropriate dose of CBZ to inform the treatment of children in Stage 2.

A cohort of eleven patients were evaluated through a review of safety and tolerability. Data presented to the DMC included the number and reason for any DLTs, laboratory safety assessments, abnormal physical examinations, pain scores and adverse events. Initially, the Stage 1 safety review [report dated 9/8/2021] was presented to the IDMC when six patients in Stage 1 reached their maximum tolerated dose or 20mg/kg. A subsequent report was presented to the DMC [25/10/2021] once the last patient on CBZ in Stage 1 reached the 6-month time point.

Following these reviews, the IDMC recommended continuation of the trial according to the current version of the protocol (Version 6.0 dated 30 June 2021) with no changes and agreed that the IMP dose regimen to be implemented in Stage 2 of the study should be 20 mg/kg.

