4.3.2 Analysis

All patients who have completed the baseline observation period and have received at least one dose of CBZ will be included in the primary analysis.

Height measurements will be displayed graphically by individual indicating measurements taken during baseline and treatment periods.

Height measurement data will be analysed using the STATA commend **xtgee** to estimate the parameters of the regression model in 4.3.1. The parameter β_3 representing the change in growth velocity will be reported together with 95% confidence interval. The Huber/White/sandwich estimator of variance will be used to obtain confidence intervals [in STATA: vce(robust)].

If fitting the growth model in section 4.3.1 is problematic, for example, lack of convergence, then a simplified analysis will be considered.

For subject *i* (*i* = 1,..,*N*), let v_{ik} denote growth velocity (a continuous response variable) measured during the baseline period (*k*=1) and the treatment period (*k*=2). Growth velocity during the baseline period for each participant will be estimated using the first available and last available measurement during the baseline period; the growth velocity during the treatment period will be estimated in a similar manner.

The model for growth velocity is:

$$v_{ik} = \beta_1 + \beta_{2i} + \beta_3 P_k + \varepsilon_{ik},$$

where β_1 , β_{2i} and β_3 are regression parameters to be estimated using simple linear regression. P_k takes the value 0 for baseline period velocities (*k*=1) and 1 for treatment period velocities (*k*=2). As for the previous GEE model, the parameter β_3 represents the change in growth velocity between treatment and baseline periods. The parameter β_3 representing the change in growth velocity will be reported together with 95% confidence interval.

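### The SAP's second analysis population is defined by dose prescribed, where the protocol defines it by doses received; the SAP does not record the change or define its average for children who stop early

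*SAP*

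**What the plan says.** Both documents name two analysis populations, and the first is the same in each. SAP 4.3.2 puts into the primary analysis "All patients who have completed the baseline observation period and have received at least one dose of CBZ", which matches the first population of protocol 11.1.

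The second differs. Protocol 11.1 takes children who have completed baseline and "have received at least 75% of planned CBZ doses over the 12 -month treatment period". SAP 4.2 takes children who have completed baseline and "have been prescribed, on average, at least 15 mg/kg of CBZ over their first 12 -months of treatment", and explains the cut as "a dose which is at least 75% of the dose recommended from Stage 1". SAP 4.3.4 repeats this definition for the sensitivity analysis of the primary outcome, its only use. The SAP cites protocol version 9.0, whose section 11.1 carries the receipt rule, but neither mentions nor justifies the change.

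Intake is nevertheless collected. SAP 3.1.6 says "Compliance will be reported as the number of missed CBZ doses reported at each visit or dose evaluation phone call", along with the percentage of the prescribed daily dose taken. Protocol 9.7 has compliance recorded on the eCRF.

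For children who do not tolerate the dose, protocol 8.8.1 and 8.8.6 add: "The inclusion of such patients in the final efficacy analysis will be discussed and evaluated case by case by the TMG", with IDMC input if required. The SAP contains no such step.

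**The concern.** The 75% figure survives from protocol to SAP but changes meaning: from the share of doses received to the size of the dose prescribed. A set built on prescriptions cannot separate a child who took the drug from one who was only prescribed it. SAP 4.3.4 is the only analysis of the primary outcome restricted by dose or exposure. In a single-arm trial with no power calculation, it is one of few internal checks on whether a change in growth velocity holds in children who had adequate drug. The protocol's version of that check, by intake, is no longer planned.

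The SAP rule is also incomplete. It does not say whether titration weeks count in the average, or how time after stopping enters. Protocol 8.9 lets a child stop treatment and stay in follow-up, so heights measured off drug could enter a set described by adequate dosing.

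**Working it through.** **Inputs.** The IDMC "agreed that the IMP dose regimen to be implemented in Stage 2 of the study should be 20 mg/kg" (SAP 1.2). For titration, "Participants will be initiated on a daily CBZ dose of 5mg/kg/day, divided into two separate doses", rising by 5 mg/kg/day every seven days to 20 mg/kg/day or the maximum tolerated dose (SAP 3.1.6). The documents give no adherence or stopping rates, so the intake levels and the week-13 stop below are assumptions.

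**The SAP's own figure.** 0.75 × 20 = 15 mg/kg. It reproduces exactly.

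**Average prescribed dose over 365 days, titration weeks counted.**
- Settled at 20: [7 × (5 + 10 + 15) + 344 × 20] / 365 = 7,090 / 365 = 19.42 mg/kg.
- Settled at 15: [7 × (5 + 10) + 351 × 15] / 365 = 5,370 / 365 = 14.71 mg/kg.
- Settled at 10: [7 × 5 + 358 × 10] / 365 = 3,615 / 365 = 9.90 mg/kg.

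**Intake in a child prescribed 20 mg/kg.** Dose taken = share taken × 19.42. Two doses a day make 730 in a year, and 75% of 730 is 547.5, so 548 doses are needed under the protocol rule.

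| Share taken (assumed) | Average taken, mg/kg | SAP set | Protocol set |
|---|---|---|---|
| 25% | 4.86 | in | out |
| 50% | 9.71 | in | out |
| 74% | 14.37 | in | out |
| 75% | 14.57 | in | in |
| 100% | 19.42 | in | in |

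The SAP column never changes because the prescribed average is 19.42 throughout. A fully adherent child settled at 10 mg/kg takes 9.90 mg/kg, nearly the same as the half-taker at 20, and is out under the SAP.

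**Stopping at week 13 from 20 mg/kg.** Weekly levels sum to 5 + 10 + 15 + 10 × 20 = 230.
- Over time on drug: 230 / 13 = 17.7 mg/kg, in.
- Over 12 months with zero after stopping: 230 / 52 = 4.4 mg/kg, out.

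If time after stopping counts as zero, reaching 15 needs 210 + 20 × (d − 21) ≥ 15 × 365 = 5,475, so d ≥ 284.25: prescription for about 285 days.

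**Titration weeks.** If they count, a fully adherent child settled at exactly 15 mg/kg averages 14.71 and misses a cut meant to represent that dose.

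**The case against.** A dose-level subset is a legitimate question where lower doses are foreseen (protocol 5.3, SAP 3.1.6), and the SAP states its basis for 15 mg/kg. Neither document says in words that the second population is meant to isolate children who took the drug. The set feeds one sensitivity analysis, and per-participant dose and compliance are reported, so a reader could examine intake informally. All of this stands. It limits the consequence and supports keeping the prescribed-dose set. It does not explain why the protocol's intake rule disappeared without comment.

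Three stronger readings are tempting but not supported.

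- *The SAP drops adherent low-dose children whom the protocol keeps.* The protocol does not define planned doses. If the term means the child's own schedule, the adherent 10 mg/kg child meets the protocol rule. If it means the amount planned at 20 mg/kg, that child has 9.90 / 20 = 49.5% and fails there too. Such children stay in the primary analysis in any case. The half-taker at 20 mg/kg fails the protocol rule on either reading.
- *Children who took nothing count as treated.* The SAP average runs over months of treatment, which presupposes a start. The secure case is the child who takes few doses.
- *Low-dose children can be removed from the efficacy result after growth has been seen.* The case-by-case sentences sit in the protocol's Stage 1 section, provide for IDMC input, and are not carried into the later SAP, which includes all dosed children who completed baseline. What remains is protocol wording that the SAP has not expressly set aside.

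**Conclusion.** The mismatch stands. In the SAP the second population has no intake condition, the protocol's has one, and the change is unrecorded. A child prescribed 20 mg/kg qualifies at any level of intake after starting. The 15 mg/kg average is undefined for a child who stops early, and the choice can move that child across the cut (17.7 against 4.4 mg/kg for a stop at week 13).

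The effect is confined to the sensitivity analysis in SAP 4.3.4. The primary population and the primary estimate are unaffected. How many children would change set cannot be known from the documents; the worked cases show how the rule behaves and do not forecast numbers. They assume the seven-day titration in SAP 3.1.6 and a 365-day or 52-week year. It would go too far to call the sensitivity analysis uninterpretable. It answers a question about dose level, and the protocol's question about intake goes unanswered. The change should be made before the final analysis.

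**What to change.** In SAP 4.2 and 4.3.4:

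1. Add the protocol's set: baseline completed and at least 75% of planned doses received over 12 months. State whether planned means the child's own schedule, and count doses after stopping as not received. Derive it from the missed-dose and percentage-taken data already reported under SAP 3.1.6.
2. Keep the prescribed-dose set as a separately labelled dose-level sensitivity analysis. State how titration weeks and time after stopping enter its average.
3. Record the prescribed-dose set as a departure from protocol 11.1, with the reason.
4. State that the Stage 1 case-by-case inclusion sentences in protocol 8.8.1 and 8.8.6 do not apply to the primary population, so that those sections and SAP 4.3.2 are reconciled.

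A single rule of at least 15 mg/kg taken is not a good substitute. It appears in neither document, still removes adherent children on lower doses, and fails a fully adherent child settled at 15 mg/kg (14.71) if titration weeks count.

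The cost is SAP wording, one derived variable and one more sensitivity analysis. Adherence records are imperfect, so the intake-based set will carry some misclassification.

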5.3 Stage 2 - Treatment

During Stage 1, the additional 29 Stage 2 participants will be recruited and will commence the 6-month observation period in preparation for the start of Stage 2. Stage 2 is a 12-month CBZ treatment stage in a population of 29 participants from multiple trial sites across the UK, and self sponsored trial sites across Europe and Australia(See Table 3. Stage 2 patients will only begin treatment after the Stage 1 safety review is completed and when an agreed safe and tolerable dose has been identified (section 8.8.6). In the case that the dosing regimen remains the same, Stage 1 participants will be included in Stage 2 analysis. In the case that the dosing regimen changes, the IDMC will be consulted about whether inclusion is appropriate. Participants who are in the Stage 2 treatment phase may be on a lower dosing regimen if they are unable to tolerate the maximum dose of 20mg/kg. The titration will need to be recorded in the patient's notes and documented in the trial MACRO database. Clinical judgement alongside clinical assessments will be used to determine if the dose must be lowered.

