8.8 Stage 1 – Dose titration and tolerability (UK only)

The dose titration stage of the trial will involve two recruiting UK sites. The trial follows a design that titrates the dose of carbamazepine (CBZ) to a pre-specified optimum, based on clinical considerations. The trial aims for all Stage 1 participants to reach a dose of 20mg/kg by the end of the 12 month stage 1 period. Clinical judgement alongside clinical assessments will be used to determine a stable dose for the patient. Stable dose will be confirmed when a participant reaches a dose of 20mg/kg or the maximum dose at which they are able to tolerate any CBZ-related side effects (their maximum tolerated dose (MTD) and has a period of at least 8 weeks with no significant IMP related adverse events/side effects).

Stage 1 participants will be treated according to the dose titration regimen outlined below and detailed in Figure 2, following the guidance stated in the Guy's and St Thomas' NHS foundation Trust's paediatric formulary and British National Formulary (BNF) for Children for use of CBZ in children with epilepsy.

Figure 2 – Overview of design of dose titration & tolerability period from month 0 to 3

- Participants will be initiated on a daily CBZ dose of 5mg/kg/day. This daily dose will be divided, and participants will be asked to take CBZ twice daily. Doses may be taken during, after or between meals, with a little liquid e.g. a glass of water. If the current dose is tolerated by participants following 7 days of treatment, patients will be instructed to increase their daily dose by 5mg/kg/day for a further seven days
- The dose level will be increased every seven days until a maximum dose of 20mg/kg/day or MTD is achieved

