4.3.4 Sensitivity analysis of primary outcome

The primary analysis will be repeated including only those participants who have completed their baseline observation period and have been prescribed, on average, at least 15 mg/kg of CBZ over their first 12 - months of treatment, i.e. a dose which is at least 75% of the dose recommended from Stage 1.

Note that some participants will have longer than 12 months of treatment. Dosing details during these extended periods of treatment will not be considered when determining if a participant is included in this sensitivity analysis. However, if a participant is included, then the participant's growth data for this extended period of treatment will be included in the analysis.

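### The 15 mg/kg cut-off for the SAP's second population counts titration weeks in the child's mean but not in the 20 mg/kg it is set against, so a child held at 15 mg/kg is left out

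*SAP*

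**What the plan says.** SAP 4.2 defines population 2 as children who completed baseline and "have been prescribed, on average, at least 15 mg/kg of CBZ over their first" 12 months of treatment. SAP 4.3.4 repeats the rule for the sensitivity analysis and glosses it as "a dose which is at least 75% of the dose recommended from Stage 1". SAP 1.2 supplies that dose: the IDMC "agreed that the IMP dose regimen to be implemented in Stage 2 of the study should be 20 mg/kg".

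SAP 3.1.6 describes the titration. "Participants will be initiated on a daily CBZ dose of 5mg/kg/day, divided into two separate doses". If seven days are tolerated, "the daily dose will be increased by 5mg/kg/day for a further seven days", and "The dose level will be increased every seven days until a maximum dose of 20mg/kg/day or MTD is achieved". Protocol 8.8 sets the same steps for Stage 1, starting from "Participants will be initiated on a daily CBZ dose of 5mg/kg/day".

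Maintenance below target is foreseen: under Protocol 5.3, children in Stage 2 "may be on a lower dosing regimen if they are unable to tolerate the maximum dose of 20mg/kg". The only dosing that SAP 4.3.4 sets aside is dosing after the first 12 months. Neither section removes the titration weeks from the mean, and neither says how the mean is rounded.

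Protocol 11.1 defines its second population differently, by receipt of three quarters or more of the doses planned for the 12 months.

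**The concern.** The gloss in the SAP treats a 12-month mean of 15 mg/kg as the same thing as 75% of 20 mg/kg. The two sides are not built alike. The child's mean includes the weeks at 5 and 10 mg/kg that every child must pass through. The 20 mg/kg is a target dose with no titration in it. Even a child who follows the schedule perfectly to 20 mg/kg averages less than 20.

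The mismatch matters most at 15 mg/kg, because titration moves in 5 mg/kg steps and 15 is the first step below target. A child held there is on exactly 75% of the recommended dose, yet falls just short of a threshold described in those terms. What is at stake is who enters the only dose-based sensitivity analysis of the primary outcome, and whether its description in the report will be accurate. With 40 children planned, each one classified differently is 1/40 = 2.5% of the sample.

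**Working it through.** **Inputs.** Recommended dose 20 mg/kg (SAP 1.2). Start at 5 mg/kg/day, rising by 5 every seven days to 20 or the maximum tolerated dose (SAP 3.1.6; Protocol 8.8). Window: first 12 months (SAP 4.2), taken here as 365 days. The mean is taken as time-weighted, sum(dose × days)/365, and compared unrounded.

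**The plan's own figure.** 0.75 × 20 = 15.0 mg/kg. This reproduces.

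**Child titrated on schedule and held at 15.** (7×5 + 7×10 + 351×15)/365 = 5370/365 = 14.71 mg/kg, below 15. A year of 360, 364 or 366 days also gives 14.71.

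**Child titrated on schedule to 20.** (7×5 + 7×10 + 7×15 + 344×20)/365 = 7090/365 = 19.42 mg/kg.

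**Like for like.** 5370/7090 = 75.7%. Measured against the scheduled regimen over the same days, the child held at 15 is above 75%.

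**What it takes to reach a mean of 15.** The first two weeks leave a shortfall of 7×10 + 7×5 = 105 mg/kg-days. Each day at 20 rather than 15 repays 5, so 105/5 = 21 days at 20 are needed. Alternatively, a steady dose from day 15 of (15×365 − 105)/351 = 15.30 mg/kg is enough.

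**Same 15 mg/kg maintenance dose, different time at 20 first:**

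| Days at 20 | Mean (mg/kg) | In population 2? |
|---|---|---|
| 0 | 14.71 | no |
| 7 | 14.81 | no |
| 14 | 14.90 | no |
| 21 | 15.00 | yes |
| 28 | 15.10 | yes |

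**Slower titration.** With 14-day steps to 15: (14×5 + 14×10 + 337×15)/365 = 5265/365 = 14.42.

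**A benchmark built the same way as the mean.** 0.75 × 7090/365 = 5317.5/365 = 14.57 mg/kg. The child at 14.71 is then in. Two edges follow:
- The lowest qualifying steady dose from day 15 is (5317.5 − 105)/351 = 14.85 mg/kg, slightly under 15.
- For a child who goes to 15 in steps of s days, the total is 5475 − 15s, so s may be at most (5475 − 5317.5)/15 = 10.5 days. The child on 14-day steps (14.42) stays out.

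**The case against.** The strongest reply is that nothing in the SAP is miscalculated. The rule concerns the average prescribed over a year, and a child who averages 14.71 did average less than 75% of 20. Read as a year-long exposure rule it is coherent, and whether titration weeks count is a choice of definition. That is fair as far as it goes: this is a mismatch between a rule and its description, not a wrong sum. But no schedule in the plan delivers a mean of 20, so 75% of 20 is not 75% of anything a compliant child could average.

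Several limits stand. Rounding to a whole mg/kg would turn 14.71 into 15 and admit the child, but no such rule is stated. Maintenance doses are not confined to four values, because Protocol 8.8.1 allows other modifications. The margin is also small: 0.30 mg/kg is 6 mg a day for a child of 20 kg (an illustrative weight), against tablets of 100, 200 and 400 mg (Protocol 9.1), so dose rounding could put a nominal 15 mg/kg child on either side. SAP 3.1.6 has each child's daily dose plotted and the maximum tolerated dose reported, so such children will be visible. Protocol 8.8.1 and 8.8.6 also leave the inclusion of lower-dose children in the efficacy analysis to case-by-case evaluation.

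A reader might infer that the set amounts to children who reached 20 mg/kg, or that a child maintained at 15 can never enter. The documents support neither. A child with one or two weeks at 20 before settling at 15 is excluded; a child with 21 days there, or on a steady 15.3, is included. A reader might also add a further loss from weight gain between the three-monthly weighings. That concerns the mg/kg delivered, whereas the rule uses the dose prescribed, and the documents give no rate of weight gain.

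**Conclusion.** The point holds as a like-for-unlike comparison in SAP 4.2 and 4.3.4. A child titrated on schedule and held at 15 mg/kg averages 14.71 and is excluded as below 75%, while reaching 75.7% of what the scheduled regimen averages. Children with the same 15 mg/kg maintenance dose are separated by whether they first spent at least 21 days at 20.

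This rests on a time-weighted mean counted from the first dose, a 365-day year, weekly steps as scheduled, and no rounding.

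The reach is limited. The set is used only in the sensitivity analysis. Under SAP 4.3.2 the primary analysis takes every child who completed baseline and received at least one dose, so a reader should not infer that the primary estimate is affected. The number of children maintained at 15 mg/kg is not given; it could be none, and the effect on the sensitivity estimate cannot be computed. The rule is still worth correcting before the analysis, so that inclusion near the threshold is not settled after the growth data are seen.

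**What to change.** In SAP 4.2 and 4.3.4, keep the time-weighted mean prescribed mg/kg over the first 12 months, but compare it with 75% of the mean that the scheduled regimen (5, 10, 15, then 20 mg/kg) would give over the same period: 0.75 × 19.42 = 14.57 mg/kg for 365 days. State that the mean is time-weighted and compared unrounded. Reconcile the definition with Protocol 11.1; the revised benchmark is closer to it, since scheduled titration doses are planned doses.

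Starting the average at day 22 and keeping 15 mg/kg looks simpler but works less well. With 14-day steps, a child who settles at 15 still has seven days at 10 after that date: (7×10 + 337×15)/344 = 14.90, still excluded. It also gives no average for a child who stops before day 22, and if the window closed when treatment stopped it could admit a child who stopped after a few weeks at 20.

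The cost is one sentence in each of two SAP sections and a changed threshold; the dosage decisions are already recorded in the eCRF (SAP 3.1.6). There is a small downside: a steady dose of about 14.85 mg/kg or more would also qualify, and a child titrated in 14-day steps to 15 (mean 14.42) would still be excluded. This changes an analysis definition only and implies no change to any dose or clinical rule.
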